
USDHHS (2016). E-cigarette Use Among Youth and Young Adults: A Report of the Surgeon General. Atlanta, GA: USDHHS, CDC, National Center for Chronic Disease Prevention and Health Promotion, Office on Smoking and Health.

2. * Describe the study hypothesis and/or research questions. Use lay language whenever possible.

The purpose of this study is to determine if abuse liability indices will be impacted by varying flavors and ECIG nicotine delivery capability (i.e., nicotine flux) among current combustible cigarette users.

We will compare abuse liability indices between three FDA authorized ECIG products that vary in nicotine flux (but are all tobacco flavor) and own brand cigarettes. We will also test the influence of ECIG flavor availability (tobacco vs. menthol) within three ECIG product classes.

We hypothesize that as nicotine flux is lowered, abuse liability indices will be lowered.

We also hypothesize that across ECIG product classes, abuse liability indices will be higher for menthol-flavored products.

3. * Describe the study's specific aims or goals. Use lay language whenever possible.

Aim 1: Compare the abuse liability of own brand (OB) cigarettes and three FDA-authorized tobacco flavor ECIGs that vary by nicotine flux.

Aim 2: Test the influence of ECIG flavor availability (tobacco vs. menthol) within each ECIG product class.

4. * Describe the scientific benefit or importance of the knowledge to be gained:

The benefits of this research are of a scientific nature. Specifically, we aim to use study results to inform our understanding of the abuse liability of ECIG liquid characteristics as well as provide information to guide the appropriate regulation of ECIGs.

In particular, the use of ECIGs has become increasingly popular, especially among individuals aged 18-24. New regulations are being targeted at this age group and need to be tested in this age group before implementation. The overarching theme of the Center for the Study of Tobacco Products is to provide regulators (FDA and others) with a suite of tools that allow them to test regulations before they are implemented to determine if those regulations will have

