1. May participate in any study interaction or intervention (Including screening, consenting, and study activities)

AND/OR

2. You obtain any data/specimens about (regardless of identifiability)

at VCU and at other sites under the VCU IRB's oversight. See the help text for additional guidance.

100

2. If this is a multi-Center Project, what is the maximum anticipated number of subjects across all sites?

N/A

3. * Provide justification for the sample size by explaining how you arrived at the expected number of participants and why this number is adequate for answering the research questions:

This study manipulates e-cigarette flavor and nicotine flux systematically, testing the hypothesis that abuse liability will be related directly to flux or flavor among a sample of cigarette smokers. Previous studies using this type of design are limited.

Thus, we calculated a sample size to achieve a power of >0.80 with $\alpha < 0.05$ and assuming a small effect size (Cohen's $f=0.20$) and moderate repeated measures correlation ($r=0.5$) in a repeated measures ANOVA with nicotine flux as within-subjects factors ($N=32$; GPower).

In this study, 36 cigarette users will attend the lab for 4 sessions: 1) own brand cigarette (always the first session), 2) NJOY Ace 2.4% nicotine ECIG (Menthol and Classic Tobacco flavor), 3) NJOY Ace 5.0% nicotine ECIG (Menthol and Classic Tobacco flavor), and 4) NJOY Daily ECIG 6% nicotine (Menthol and Extra Rich Tobacco).

We hypothesize that flux will be positively associated with willingness to pay (drug purchase task) and willingness to substitute e-cigarettes for own brand cigarettes (cross-product drug purchase task), and inversely to price sensitivity (drug purchase task) for all smokers.

We hypothesize that within class, menthol flavored products will be positively associated with willingness to pay (drug purchase task) and willingness to substitute e-cigarettes for own brand cigarettes (cross-product drug purchase task), and inversely to price sensitivity (drug purchase task) for all smokers.

It is possible that we would consent up to 100 participants in order to obtain 36 participants who complete the entire study.

4. * List the study inclusion criteria:

All participants must be healthy (determined by self-report), at least 18 years old (verified by photo ID), willing to provide informed consent, and attend the lab. Participants must agree to use designated products according to the study protocol.

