Tobacco Cessation Resources. A brief handout containing information about tobacco cessation and available resources will be provided to all participants who consent to this study. Participants are not required to take the handout. This handout will be given at the end of their study participation (at screening if ineligible, at the end of their last study session, or via email if they self-withdraw or are withdrawn by the PI/medical monitor). We provide this information as it may assist individuals who are considering quitting tobacco now and/or quitting tobacco in the future.

Data analysis. Subjective, physiological, and behavioral data will be prepared as reported elsewhere (e.g., [name] et al., 2017; Rusted et al., 1998; [name] et al., 2010). Elasticity is estimated using an exponential demand function with nonsystematic DTP data excluded based on two criteria: trend, or whether the participant had a general decrease in consumption from the lowest to highest price; and bounce, or whether a participant reported higher consumption at sequential higher prices (Stein et al., 2015). In general, analysis will involve a mixed (between- and within-subject) ANOVA. Demographic data will be examined to determine if there are significant between-group differences on measures that may be related to study outcomes. Unexpected between group differences will be considered as potential covariates in the primary analysis (see Evans et al., 2006). Statistical analyses may utilize regression, ANOVA, or mixed linear models. Adjustments for sphericity violations and post-hoc testing using Tukey's HSD or planned contrasts with Bonferroni corrections will be used (Keppel, 1991). Based upon the type and amount of missing data, we may use accepted techniques such as multiple imputation (Allison, 2001).

8. * The IRB only reviews research activities, so indicate for each of the study activities described in the question above or in the protocol which activities are:

- Being performed exclusively for research purposes (i.e. they would not otherwise be done apart from this study) **VERSUS**.
 - Alterations of routine activities/procedures (e.g. the study is altering the timing, frequency, method, location, amount, etc.) **VERSUS**.
 - Being done for other purposes and whose data/results will be used secondarily in the study (e.g. standard medical or psychological tests, routine education practices, quality improvement initiatives, etc.).
- See the help text for additional guidance

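### Single-step Bonferroni for planned contrasts is valid, but Holm's step-down procedure gives the same family-wise protection and never rejects less; the plan should name Holm and define the Aim 2 family

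*Combined protocol and SAP*

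**What the plan says.** The only multiplicity statement is in Study Procedures, item 7, under Data analysis. It offers Tukey's HSD for post-hoc tests as one option; the other is that "planned contrasts with Bonferroni corrections will be used". No step-down version is named. The text does not say which contrasts are planned, how many form a family, or whether the correction runs within one outcome or across outcomes.

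Aim 2 (Background, Rationale and Goals, item 3; repeated under Study Procedures, item 2) is to "Test the influence of ECIG flavor availability (tobacco vs. menthol) within each ECIG product class". There are three classes: NJOY Ace 2.4%, NJOY Ace 5.0% and NJOY Daily 6%. The matching hypothesis (item 2) is that "across ECIG product classes, abuse liability indices will be higher for menthol-flavored products", and the sample size justification restates it as a within-class expectation.

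That justification (Study Population, item 3) assumes f = 0.20, a repeated-measures correlation of 0.5, alpha 0.05 and power above 0.80, for a repeated measures ANOVA on nicotine flux. It arrives at N = 32 and plans 36 completers. It contains no calculation for flavor.

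**The concern.** Read with the aims, the natural planned contrasts for Aim 2 are three differences per outcome: menthol minus tobacco in each class. Bonferroni tests each of them at 0.05/3 = 0.0167, whatever the other two show. Holm starts at the same threshold and relaxes it once a contrast has been rejected: 0.05/3, then 0.05/2, then 0.05. It controls family-wise error under any dependence between the tests, as Bonferroni does.

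The other named option, Tukey's HSD, fits Aim 2 poorly. It is built for all pairwise means. Six e-cigarette conditions give 6 × 5 / 2 = 15 pairs, and Aim 2 needs three of them.

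Aim 2 asks for an answer in every class, and the results are meant to inform product regulation. A class could be reported as showing no flavor effect only because the less powerful of two equally protective corrections was used.

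**Working it through.** **The plan's own figure.** For a within-subject ANOVA with m levels, λ = f²Nm/(1 − r), with df m − 1 and (N − 1)(m − 1). The number of levels is not stated. At N = 32:
- m = 4 (own brand plus three e-cigarettes): λ = 0.04 × 32 × 4 / 0.5 = 10.24, power 0.753; 80% needs N = 36.
- m = 3 (e-cigarettes only): λ = 0.04 × 32 × 3 / 0.5 = 7.68, power 0.676; 80% needs N = 42.

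So N = 32 does not reproduce for either reading of the flux factor. That is a separate matter; what follows uses the 36 completers.

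**Inputs for the flavor contrasts**
- From the documents: N = 36 (non-completers are replaced), alpha 0.05, f = 0.20 and r = 0.5.
- Assumed: a family of three contrasts on one outcome; the flux values of f and r apply to flavor; two-sided paired t-tests.
- Effect size: for two levels d = 2f = 0.40, so d_z = d / √(2(1 − r)) = 0.40 / 1 = 0.40. Noncentrality is 0.40 × √36 = 2.4 on 35 df.
- Correlation: with one common r of 0.5 and equal variances, the covariance of two class differences is r − r − r + r = 0 (in units of the variance), so the contrasts are uncorrelated. A correlation of 0.5 is a sensitivity case.

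**Power of one test at each threshold (noncentral t)**
- A, at 0.05/3: 0.463
- B, at 0.05/2: 0.529
- C, at 0.05: 0.646

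**All three effects real and equal, contrasts independent**
- Bonferroni, per contrast: A = 0.463. All three: 0.463³ = 0.099.
- Holm, all three: every p-value must be at most 0.05, at least two at most 0.025, and at least one at most 0.0167. This gives B³ + 3B²(C − B) − (B − A)³ − 3(B − A)²(C − B) = 0.244. Simulation with 600,000 replicates also gives 0.244.
- Holm, per contrast (same simulation): 0.542.
- At least one rejection, both methods: 1 − (1 − 0.463)³ = 0.845.
- Family-wise error with no real effect, both methods: 1 − (1 − 0.05/3)³ = 0.049.

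The gain is 7.9 points per contrast and 14.5 points for all three.

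**Sensitivity at N = 36**

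| Scenario | Per real contrast, Bonferroni → Holm | All three, Bonferroni → Holm |
|---|---|---|
| d_z 0.40, three real, correlation 0 | 0.46 → 0.54 | 0.10 → 0.24 |
| d_z 0.40, three real, correlation 0.5 | 0.46 → 0.54 | 0.21 → 0.37 |
| d_z 0.30, three real, correlation 0 | 0.25 → 0.29 (+3.4 points) | 0.016 → 0.058 |
| d_z 0.50, three real, correlation 0 | 0.69 → 0.79 (+10 points) | 0.32 → 0.55 |
| d_z 0.40, two real | 0.46 → 0.50 (+3 points) | not applicable |
| d_z 0.40, one real | 0.46 → 0.47 (+0.2 points) | not applicable |

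With two real effects at d_z 0.40, the error rate on the null contrast is about 0.017 under Bonferroni and 0.03 under Holm, both below 0.05.

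**With no correction at all**, power is 0.646 per contrast and 0.646³ = 0.27 for all three. Reaching 80% per contrast without correction would take about 52 participants.

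**The case against.** Bonferroni is valid, standard and easy to explain, and it comes with matching simultaneous intervals. Nothing in the plan is wrong or inflated because of it. That stands in full: this is a matter of efficiency.

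The family is inferred. The plan leaves Tukey and contrasts as alternatives, allows regression, ANOVA or mixed models, and lists five purchase-task outcomes plus cross-price elasticity without saying how they are grouped. The hypothesis across classes could be tested by one flavor main effect, with no three-way correction. This also stands. It means that the size is conditional, and that swapping one word without defining the family would leave the main ambiguity in place. It does not touch the ordering of the two methods: for any family, Holm rejects at least what Bonferroni rejects.

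Three stronger readings are tempting, and the documents do not support them. A reader might infer that the correction is what chiefly keeps Aim 2 from succeeding. It is not: with no correction, power at 36 completers is only 0.65 per contrast, so sample size and effect size bind first. A reader might take 8 and 15 points as the loss in general. Those figures need three equal real effects at d_z = 0.40, and the gain nearly vanishes if only one class shows an effect. And a reader might treat f = 0.20 as the plan's expectation for flavor. It is stated for flux only.

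**Conclusion.** The point holds as a cheap improvement. Holm's dominance over single-step Bonferroni at the same family-wise error rate needs no assumption about the data. Its size does. Under the assumptions listed, with all three effects real and equal, power rises by about 8 points per contrast and by about 15 points for all three (16 if the contrasts correlate 0.5). At d_z = 0.30 those gains are about 3 and 4 points.

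All three effects being real is the investigators' own hypothesis, so the favourable case is a relevant one, but it is not assured. Holm leaves power near 54% per contrast and does not give Aim 2 80% power.

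**What to change.** In Study Procedures, item 7, Data analysis, name the Holm step-down correction in place of Bonferroni for planned contrasts. Add one sentence: for Aim 2 the family is the three menthol-minus-tobacco contrasts of an outcome, ordered by p-value and compared in turn with 0.05/3, 0.05/2 and 0.05, stopping at the first failure. The same sentence settles that Aim 2 uses these contrasts and not Tukey's HSD. Make the change before outcome data are analysed.

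The cost is a phrase and a sentence, with no added participants, visits or data. The one drawback is that Holm has no equally simple matching simultaneous intervals. Bonferroni intervals at 100 × (1 − 0.05/3) = 98.3% can still be reported, with a note that they may include zero for a contrast that Holm rejects.

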****The IRB will expect studies to operationalize all selected checkboxes into the conduct of the research.**

To elaborate on any response, also click the "Other Protections" checkbox to provide further explanation in the last free-text question.

Read the entire page before filling out the form.

1. * Protections when conducting one-on-one in-person interventions or interactions (for groups see Q2 below):

- ☒ Conducting study activities in locations that maximize privacy (limited people around, closing doors, drawing drapes around beds, monitoring voice volume, etc.)
- ☐ Verifying identity before discussing personal information.
- ☐ Asking the participant if they are comfortable answering questions in that location
- ☐ Asking the participant if they are comfortable with having other people present (if any)
- ☐ Moving away from other people when conducting activities in public spaces or offering a private space
- ☐ Offering other options of ways to respond to sensitive questions (i.e. pointing, clicking, or writing) if uncomfortable verbally responding
- ☐ Using generic signs on research rooms and spaces, particularly for research on stigmatizing or sensitive topics
- ☒ Other protections not listed in this question – describe below
- ☐ N/A – study has no in-person interventions or interactions with participants

2. * Protections when conducting group interventions or interactions:

- ☒ Conducting study activities in locations that maximize privacy (limited people passing by, closing doors, monitoring voice volume, etc.)
- ☐ Moving to a more private area to answer questions or to discuss concerns
- ☐ Discussing privacy with the participants and the importance of not talking outside the group about what other people say during the group session
- ☐ Allowing participants to use a pseudonym or limiting use of individuals' names during the group activity
- ☐ Asking everyone in a public group setting (e.g. classrooms, workshops) to turn something in (blank or filled) so participants do not have to self-identify when turning in materials
- ☐ Collecting paper forms in a closed box or envelope rather than passing to others or leaving in an open area
- ☒ Limiting participant identifiers that would be visible on paper documents (i.e. using study IDs instead of direct identifiers)
- ☐ Allowing people to distance themselves from other participants during group activities
- ☐ Offering other options of ways to respond to sensitive questions (i.e. pointing, clicking, or writing instead of speaking)

- ☐ Using generic signs on research rooms and spaces, particularly for research on stigmatizing or sensitive topics
- ☐ Ensuring non-participating individuals are not captured on recordings or in photos
- ☐ Other protections not listed in this question – describe below
- ☐ N/A – study has no group interventions or interactions

3. * Protections when conducting remote interventions or interactions (e.g. phone, text, email, video-conference, tele-health, online, etc.):

- ☒ **Conducting study activities in locations where study staff can maximize their own privacy (limited people around, closing doors, monitoring voice volume, etc.)**
- ☐ Leaving/sending generic messages that avoid using study and participant identifiers, such as names, study titles, clinics, study topics, etc.
- ☒ **Obtaining permission prior to sending text messages**
- ☐ Advising the participant to move to a location where they are comfortable answering questions and will not be overheard - incorporate this instruction into your study materials
- ☐ Advising online participants to complete the activity at a time and location where they will be comfortable answering questions - incorporate this instruction into your study materials
- ☐ Ensuring non-participating individuals are not captured on recordings or in photos
- ☐ Offering other options of ways to complete the activity (i.e. online, paper, phone) if more privacy is desired
- ☐ Offering a way to save and return later to the online activity if privacy is compromised
- ☐ Other protections not listed in this question – describe below
- ☐ N/A – study has no remote interventions or interactions with participants

4. * Protections when mailing study materials to/from participants:

- ☐ Obtaining permission to mail study materials
- ☐ Confirming/verifying the accuracy of addresses before mailing items
- ☐ Ensuring the participant is able to personally receive mailed materials and has a way to protect their own privacy if they do not want others to know they are receiving research communications (i.e. notifying participants of when to expect it)
- ☐ Using return address labels and document headers that avoid study identifiers, such as study names, clinics, study topics, etc.
- ☐ Avoiding or limiting use of participant identifiers and health information on mailed documents (i.e. using study IDs instead of direct identifiers)
- ☐ Providing a return mailing address label or pre-addressed envelope to ensure returned items are sent to the correct address
- ☐ Communicating receipt of mail from participants and/or asking them to notify you when they mail it to ensure study documents are not lost in transfer
- ☐ Offering other options of ways to complete the activity (i.e. by phone or online) if desired
- ☐ Other protections not listed in this question – describe below
- ☒ **N/A – not mailing any materials to/from participants**

5. * Protections when analyzing or disseminating study data **Applicable to all studies*:*

- ☒ **Working only in locations where the study team can ensure privacy (not working in close proximity to non-study personnel, closing doors, closing/putting away documents/files before leaving, etc.)**
- ☒ **Securing physical materials only in locations that ensure privacy (access limited to authorized study personnel)**
- ☒ **Only sharing data/specimens in accordance with the Sharing Plan outlined in this smartform**
- ☐ Obtaining explicit parental permission before disseminating or sharing recordings or photos of children
- ☐ Blurring/redacting/hiding faces and other identifiable features/marks (tattoos, scars, birthmarks, distinctive voice, etc.) in recordings or photos prior to disseminating or sharing
- ☐ Only publishing or presenting aggregate results or findings (i.e. no individual-level information)
- ☐ Taking additional steps to protect participant identities when publishing or presenting individual-level information, quotations, results, images – describe below
- ☐ Other protections not listed in this question – describe below

6. Describe any other way(s) that the research team will protect participants' privacy. See the help text for additional guidance.

Participants' privacy and comfort will be addressed throughout the course of the study. During the intake process and session, participants will be seated in a private room. All study procedures will take place behind closed doors. We will use Zoom (like an intercom) to communicate with participants from outside of the session room, but will not use a camera for the computers in the session rooms, nor will the participants' name be entered into Zoom. We will also use a password-protected Zoom session. Participants will be informed that they may withdraw from the research study should they find any research procedures unacceptable. All participants and data will be treated with professional standard of confidentiality. Data are identified by numeric code only and stored under double lock or in REDCap. Participants' names are not directly linked to data. Briefly, a numeric code is assigned to each participant when they provide informed consent, and the part of the numeric code relates to the order in which the individual consented. This numeric code appears on all data. Access to the key and the consent documents is restricted to study investigators and staff: these individuals perform the informed consent and conduct the study with the participants so they already know who the participants are and observe the participants as data are collected. Participants' research-related information will be withheld, consistent with the law, unless permission is given to release such information. Effectiveness is indexed by previous experience: we have used these procedures for over 20 years and have not had a single incident in which a participants' confidential information has been compromised.

In addition, the way in which the referral program will be administered (with participants who complete this study being given cards with alphanumeric codes linked to their names/e-mail addresses) reduces the risk of a loss of privacy, as the original participant will not be told who brought in the card(s).

Data Confidentiality and Storage

Confidentiality refers to the way private, identifiable information about a participant or defined community is maintained and shared. It describes how the study's research materials (data, specimens, records, etc.) are protected from unauthorized access.

Instructions for this page:

Select all the ways that the research team will keep the study materials and data confidential throughout the course of the study. Not all will be applicable to every study.

To elaborate on any response, also click the "Other Protections" checkbox to provide further explanation in the last free-text question.

Read the entire page before filling out the form.

1. * Protections for paper research materials:

- ☒ Maintaining control of paper documents at all times, including when at an off-campus location
- ☒ Limiting or avoiding use of participant identifiers on paper documents (i.e. using study IDs instead of direct identifiers)
- ☒ Storing paper documents in a secure location accessible only to authorized study personnel
- ☐ Promptly transcribing, scanning, or abstracting data from paper into electronic platforms with destruction of the paper copy
- ☒ Proper destruction of paper records (and obtaining prior permission when required) in accordance with VCU Records Management policies
- ☒ Other protection not listed in this question – describe below
- ☐ N/A – no paper research materials

2. * Protections for research specimens:

- ☒ Maintaining control of specimens at all times, including when at an off-campus location
- ☒ Storing specimens in a secure location accessible only to authorized study personnel
- ☒ Labeling specimens with subject ID or other coded information instead of direct identifiers
- ☒ Final destruction of specimens will be in accordance with VCU policies and specimen containers will be devoid of any identifiable information
- ☐ Other protection not listed in this question – describe below
- ☐ N/A – no research specimens

3. * Protections for electronic files/data - See <https://ts.vcu.edu/about-us/information-security/data-management-system/>

- ☒ *Required for all studies* Use VCU-approved methods of data storage, transmission, and transfer (see <https://dms.vcu.edu>)
- ☒ Remotely accessing VCU network storage to store data when at off-campus locations
- ☒ Ensuring unauthorized individuals who might share a device do not have access to study materials (e.g. individual logins, separate accounts)
- ☒ Using VCU-approved data collection tools and apps (e.g. REDCap) and storing exported analysis files in VCU-approved storage locations (see <https://dms.vcu.edu>)
When using non-VCU-approved electronic data collection tools, storage locations, data transfer platforms, and mobile apps (e.g. Dropbox, Box, Survey Monkey, Fitbits, novel apps, multi-site data collection platforms):
 - consulting with VCU Information Security on proper data management (see <https://ts.vcu.edu/askit/essential-computing/information-security/>);
 - advising participants about the terms of use and privacy policies of those sites/apps;
 - limiting or avoiding use of identifiers; and
 - removing data promptly from the external location after transferring it to a VCU storage location
- ☐
- ☒ De-identifying the research data by replacing subjects' names with assigned subject IDs
- ☒ Storing the study's linkage key in a password-protected and VCU-approved storage location (see <https://dms.vcu.edu>)
- ☐ When analyzing particularly sensitive information, using computers that are unconnected from the internet.
- ☒ Proper destruction of electronic records (and obtaining prior permission when required) in accordance with VCU Records Management policies

☒ Other protection not listed in this question – describe below

4. * Protections for computers and research devices/apps that are provided to participants for use in the study and taken out of the lab (i.e., giving participants a phone or iPad to take home, wearable trackers, apps, etc.):

- ☐ Transferring data promptly from the device/app given to the participant to a VCU storage location
- ☐ Setting strong passwords on computers and research devices (when applicable) that leave VCU with participants
- ☐ Device/app set up by VCU Information Security
- ☐ When providing devices or mobile apps to children, informing parents about the settings and how to manage them (if applicable), internet access, and any other installed apps on the device
- ☐ Other protection not listed in this question – describe the device/app and protection below
- ☒ N/A – no computers or devices/apps being provided for participant use outside the lab

5. * Protections for email/online communications

- ☒ Only using VCU/VCU Health email addresses for study-related communications
- ☒ Only using VCU/VCU Health–approved methods of teleconferencing or video conferencing (e.g. Zoom) (for studies involving HIPAA, contact VCU or VCU Health Information Security [as appropriate] about HIPAA-compliant systems)
- ☒ Other protection not listed in this question – describe below
- ☐ N/A – no email/online communications

6. Specify any other places where this study's paper and electronic research data and/or physical specimens will be stored and any other ways they will be secured from improper use and disclosure.

See the help text for additional guidance.

Any paper based records will be kept in a locked cabinet in the CSTP lab in a locked room with entry to the lab secured by a keypad and only accessed by authorized study personnel.

An electronic copy of each consent form will be stored in Veeva Site Vault per new requirements for clinical studies.

All computers and storage devices will be kept in locked cabinets and/or within locked laboratory rooms. Electronic records will be made available only to those personnel in the study through the use of access controls (passwords). Identifiers will be removed from study-related data and data will be coded with a key stored in a separate, secure location. Electronic data (with study IDs only) is stored in REDCap and/or in excel spreadsheets that are saved either on hard drives and/or a VCU server. Data from the online registry, as well as the in-person screen and from sessions will be stored in and can only be accessed through the password-secured system REDCap. Only approved CSTP staff, faculty, and students will have keys and/or electronic access to this information.

Identifiers will be removed from study-related data and data will be coded with a key stored in a separate, secure location in a locked cabinet. All web-based surveys will have data secured via passwords. De-identified data will be transferred to secure servers that are password protected for data cleaning and analysis. No data will be stored under any other departments.

Some data are recorded using software separate from REDCap. These data are stored on password protected computers and backed-up on secure datakeys that require a password (IronKey).

Software types are as follows:

REDCap for self-report data, including baseline and session measures which include subjective questionnaires, and some abuse liability measures (see the document "Drug Purchase Tasks (DPT)")

Hyperterminal is used to collect physiological data. The data file is stored locally, under a username and password protected profile. It is then copied to secure storage locations (such as Ironkey or R-Drive) after each session.

The Minute Discounting Task (see, 'Baseline Discounting Task - MDT' document) is collected at baseline or in-person screening visits via Qualtrics. Data is stored within Qualtrics under usernames and passwords assigned to some lab staff.

Urine samples are labeled with participant code numbers and stored in a -80 degree freezer in a locked laboratory space. The samples are stored separately from identifying information (consent forms).

7. * If research data/specimens will be sent/released to person(s) or group(s) outside of the VCU study team or the PI's department for the conduct of this protocol (not for future sharing),

1) identify the data/specimen recipient(s) along with their VCU department or other institutional or organizational affiliation(s).

2) give a description of what identifiers and/or codes will accompany the data/specimens.

If data/specimens are not being sent/released outside of the VCU study team or the PI's

department, state that:

Data with identifiers will not be released to any person or group outside the study team.

8. * Select all identifiers that will be collected at any time as part of this study (including for recruitment, data gathering, data analysis, etc.), even if the data will eventually be anonymized:

- ☒ Names
- ☒ Geographic Locators Below State Level
- ☒ Social Security Numbers
- ☒ Dates (year alone is not an identifier)
- ☐ Ages over 89 (age under 89 is not an identifier)
- ☒ Phone Numbers
- ☐ Facsimile Numbers
- ☒ E-mail Addresses
- ☐ Medical Record Numbers
- ☐ Device Identifiers
- ☐ Biometric Identifiers
- ☐ Web URLs
- ☐ IP Addresses
- ☐ Account Numbers
- ☐ Health Plan Numbers
- ☐ Full Face Photos or Comparable Images
- ☐ License/Certification Numbers
- ☐ Vehicle ID Numbers
- ☒ Other Unique Identifier
- ☐ No Identifiers
- ☐ Employee V#

9. If "Other Unique Identifier" was selected above, describe the identifiers:

Participant ID.

10. * If the study will code (i.e. de-identify) the research data by replacing subjects' names and/or other identifiers with assigned subject IDs, explain the following aspects of the coding process:

- The process for how subject IDs will be generated/assigned (e.g. random, sequential)
- Whether there will be a key that links the subject ID with direct identifiers. If there will be no linkage key, state that.

If a key will be created, describe

- The place where the key will be stored
- The role(s) of all individuals who will have access to the key
- When the key will be destroyed

See the help text for guidance.

Data are identified by numeric code only. Participants' names are not directly linked to data. Briefly, a numeric code is assigned to each participant when they provide informed consent, and the numeric part of the code relates to the order in which the individual consented. This participant numeric code appears on all subsequent documents/data forms. A key is maintained in the study binder so that we can demonstrate that a particular data set is associated with a particular consent document. The key and consent documents are stored separately from each other and separately from all data (under double lock or in REDCap). Access to the key and the consent documents is restricted to study investigators, staff, and students: these individuals perform the informed consent and conduct the study with the participants, so they already know who the participants are and observe the participants as data are collected. Data keys will be destroyed at the end of the study once the minimum time required for data retention has been met per VCU Data Retention Policy and/or sponsor retention requirements. De-identified data may be stored indefinitely.

Data Retention

1. * Select all of the ways that individually identifiable information obtained during pre-screening and/or screening will be handled for individuals who DO NOT qualify for the study:

- ☐ N/A - study does not require screening procedures
- ☐ Immediately destroy the information and identifiers (no data collected)
- ☐ Immediately destroy the identifiers connected with the data (anonymization)
- ☐ Store until the end of study & then destroy
- ☐ Use as "screening failure" data by members of the study team
- ☐ Provide to others outside of the research team (with the participant's permission)
- ☐ Request permission from participant to maintain and use the identifiable information
- ☒ Other

2. If Other, explain how the information will be handled.

All in-person screening procedures occur after participants have consented to the full study. All data collected may be included in reports/presentations/publications including reasons for screening failure among enrolled participants.

3. * Will participants be able to withdraw their data (paper, electronic, or specimens) from the study (e.g. ask that it be destroyed or returned) if they no longer wish to participate? (FDA-regulated studies should select No – see help text)

- ☐ Yes
- ☒ No

4. * What will happen to the research materials (e.g. data, specimens, documents, etc.) when the research has been completed?

- ☒ Stored indefinitely with identifiers removed
- ☐ Stored indefinitely with identifiers attached
- ☐ Destroyed at the end of study once the minimum time required for data retention has been met per VCU Data Retention Policy and/or sponsor retention requirements
- ☐ Destroyed when notified by sponsor but not less than the minimum time required for data retention per VCU Data Retention Policy
- ☐ Other

5. * Will audio/video recordings and full face photographs be destroyed?

- ☐ Yes
- ☒ No

6. If yes, describe at what point and how recordings will be destroyed:

7. If no, explain why the recordings need to be maintained:

There will be no recordings.

Sharing Plan

This page addresses times when investigators may be required to share information about participants or may desire to share their research information/specimens with the aim of advancing science. This page creates a plan for when and how information/specimens could be shared.

Try to anticipate all reasonably foreseeable sharing so that the consent document can also reflect that information. However, it is acceptable to amend this page later and explain either how re-consent of previously and currently enrolled participants will occur or why re-consent should not be required.

The IRB reviews this page against the consent document (if one exists) to demonstrate the ethical principle of Respect for Persons by confirming that plans for sharing do not go against what participants would understand about the use of their data/specimens.

The IRB also ensures there are adequate protections for the privacy of participants and the confidentiality of participants' data/specimens when data is shared with others.

1. * Is it likely investigators could discover information about child/elder abuse or neglect that would require mandatory reporting by the investigators or staff?

The Code of Virginia requires that most medical personnel and all employees of institutions of higher education report suspected child/elder abuse or neglect.

- ☐ Yes
☒ No

2. * Is it likely investigators could discover a previously unknown reportable disease or condition that would require mandatory reporting by the investigators or staff (i.e., HIV , coronavirus, hepatitis, etc.)?

- ☐ Yes ☒ No

3. * Will the sponsor or investigator obtain a Certificate of Confidentiality for this study?

